5.8 Concomitant Medications and Therapy

All concomitant medications and therapies used during the trial will be documented in the eCRF including name of the medication, date of administration and its duration, and indication for use.

Over-the-counter (OTC) anti-diarrheal medications, NSAIDs (with the exception of acetaminophen and paracetamol) and opioid analgesics are prohibited during the study. For further detail, please refer to Section 4.3 of the protocol. Use of prohibited concomitant medications will be considered a major protocol deviation and the subjects will be withdrawn from the study; and will be excluded from the per protocol (PP) analysis set.

6. Study Procedures

6.1 Schedule of Events

A schedule of study procedures is provided in Table 1.

Table 1 Schedule of Events

	Screening, Randomization and Treatment	Treatment			TOC
	Day 1	Day 2	Day 3 ^a	Day 4 ^b	5, 6 or 7 ^c
	Visit 1		Visit 2		Visit 3
Assessments					
Informed consent, I/E criteria	X				
Demographic information	X				
Medical history	X				
Prior/concomitant medications	X		X		X
Physical examination	X				X
Vital signs	X				X
Stool sample for culture and O&P	X				X ^f
Hematology/chemistry panel	X				X
Urinalysis	X				X
Urine drug screen	X				
Pregnancy test (urine) ^d	X				X
Randomization	X				
Telephone call			X		
Study drug dosing	X	X	X	X	
Daily study diary completion ^e	X	X	X	X	X
Adverse events	X		X		X

TOC = test of cure; I/E = inclusion/exclusion; O & P = ova and parasites

^a Visit 2 assessment should be done by telephone (after the subject has taken about 5 doses); the subject should be contacted by a member of the study team.

^b If a subject takes 3 doses of study drug on Day 1, then study drug should be completed on Day 3, otherwise the final doses will be taken on Day 4.

^c Visit 3 should occur 24 to 72 hours after the last dose of study drug. If a subject does not return for the scheduled TOC visit, a telephone call should be made and efficacy and safety data (same as Visit 2) should be collected for Visit 3.

^d Female subjects of child-bearing potential only.

^e Study drug diary completion will begin on Study Day 1 and end on last study visit. Diary completion includes recording of temperature if a subject feels feverish; (a thermometer should be provided to each subject by the site), date/time of study drug each dose; date, time and consistency of stool; as well as enteric symptoms described in protocol

^f In case stool sample collection not possible at visit 3, a rectal swab will be collected.

6.2 Screening, Randomization and Treatment Visit

Visit 1/Day 1:

When a suitable candidate is identified, the investigator or designated healthcare professional will ask the subject about their willingness to be included in the clinical trial.

The subject is to be informed verbally and in writing about the nature, risks, benefits, and expectations of participating in the clinical trial and a copy of the subject informed consent form is to be given to the subject in the appropriate language. The subject informed consent form is to be signed by the subject and by the attending investigator/ designee, prior to proceeding with the screening activities. The subject number should be assigned at the time of starting the consent process.

The following observations/procedures are to be performed/checked:

- Check of inclusion/exclusion criteria
- Gender, age, race
- Complete medical history
- Brief physical examination including vital signs (body temperature, blood pressure, and pulse) and body weight and height
- Review of the use of previous/concomitant treatments for any other clinical condition(s)
- Stool sample for culture (at a minimum, pathogenic *E. coli*) and O&P (Ova and Parasites)
- Blood sample for hematology/chemistry panel
- Urine sample for urinalysis and urine drug screen
- Urine pregnancy test for WOCBP
- Review of AEs

Eligible subjects will be randomized and the first dose of study drug should be preferably administered under unblinded study staff/independent dispenser supervision at the clinic. Subjects should be suggested to start the first dose of the study drug only after providing the stool sample. [REDACTED]

[REDACTED] Subjects will be given a study drug diary, a thermometer and record the following for 5 days, beginning on Study Day 1:

- Date and time of each dose
- Date, time, and consistency of each stool
- Temperature (if feeling feverish)
- Enteric infection symptoms:
 - abdominal pain or cramps,
 - excessive gas/flatulence,
 - nausea,

- vomiting,
- fecal urgency,
- blood and/or mucus in the stool,
- tenesmus

Subjects will be observed for the occurrence of AEs after informed consent is signed.

6.3 Treatment

Days 2 to 4

Subjects are to take 1 study drug tablet TID (morning, noon and evening) for 3 consecutive days for a total of 9 doses. Subjects who take 3 doses of study drug on Day 1 (i.e., those randomized early in the day on Day 1) will complete study drug on Day 3; other subjects will receive the last dose of study drug on Day 4. Subject will complete study diary until last study visit day, beginning on Day 1. Subjects will record the following in the study diary:

6.4 Telephone Follow-Up

Visit 2/Telephone Visit (Day 3)

On study Day 3 (after about 5 doses), subjects should be contacted by a member of the study team to undergo a telephone follow-up. Subjects will be asked about their AEs, concomitant medications and general health as well as their diary entries (see Section 6.3).

6.5 Test of Cure

Visit 3 (Day 5, 6 or 7)

Visit 3 will be the TOC visit and should be scheduled 24 to 72 hours after the last dose of study drug (i.e., after taking about 9 doses during the duration of the study). The following procedures are to be performed/checked:

- Stool sample for culture and examination
- Blood sample for hematology/chemistry panel
- Urine pregnancy test for WOCBP
- Brief physical examination including vital signs (body temperature, blood pressure, and pulse) and body weight and height
- Review of the use of concomitant treatments for any other clinical condition(s)
- Review of AEs
- Study medication compliance
- Return of unused study medication.

Subjects are to complete the study diary from day 1 until last study visit day.

If the stool sample collection is not possible at Visit 3, a rectal swab will be collected.

Note: If a subject does not return for the scheduled TOC visit (Visit 3; 24 to 72 hours after last dose of study medicine) then a telephone call should be made by the site and all the efforts should be made to collect efficacy and safety data for Visit 3. This data should be entered in eCRF for Visit 3 records.

6.6 *Unscheduled Visits and Early Discontinuation Visit*

An Unscheduled Visit is allowed at any time, for any reason, if in the Investigator's opinion it is warranted. If the Unscheduled Visit is due to an AE, the Investigator will determine whether additional visits are needed.

If a subject is discontinued from the study during an Unscheduled Visit, the Unscheduled Visit will be referred to as an Early Discontinuation Visit and all procedures scheduled for Visit 3 will be performed. If the Unscheduled Visit is not an Early Discontinuation Visit (i.e., the subject will continue to take part in the study), then study procedures will be performed at the discretion of the investigator, with the exception of the collection of IMP and subject diaries from subjects.

If the subject's condition has worsened to the degree that it is unsafe for the subject to continue in the study, the subject may be discontinued from the study as treatment failure and a standard of care treatment may be advised at the Investigator's discretion.

7. Efficacy and Safety Assessments

7.1 Methods of Assessment

All eligible subjects will be screened and randomized at Visit 1. The first dose of study drug should be preferably administered under the supervision of unblinded clinical staff/independent study dispenser at the clinic immediately after randomization. Subjects are provided with a study diary to record study drug doses; time and characteristics of each bowel movement; and enteric symptoms for 5 days.

7.2 Primary Efficacy Parameter

The primary efficacy endpoint will be clinical cure rate on TOC Visit (Study Day 5, 6 or 7).

Clinical cure is defined as either of the following:

- No stools or only formed stools within a 48 hour period and no fever, with or without other enteric symptoms, OR
- No watery stools or no more than two soft stools passed within a 24 hour period with no fever and no other enteric symptoms except for mild excess gas/flatulence.

In addition, clinical deterioration by Study Day 5 or failure to achieve formed stool in ≤ 3 days is a clinical failure.

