4.1 Inclusion Criteria

Subjects must meet all of the following inclusion criteria:

1. Be adult male or nonpregnant female aged ≥ 18 years non-indigenous travelers (e.g., visiting students/faculty or international tourists) affected by naturally acquired acute diarrhea. Diarrhea is defined as the passage of at least 3 episodes of unformed stools in a 24-hour period. Stools are classified as formed (retains shape), soft (assumes shape of container), or watery (can be poured). When using this classification, both soft and watery stools are unformed and abnormal.
2. Have at least 3 episodes of unformed stools recorded within the 24 hours immediately preceding randomization (screening and randomization should occur as closely as possible on the same day, i.e. Day 1).
3. Have at least one of the following signs and symptoms of enteric infection:
 - a. abdominal pain or cramps
 - b. nausea
 - c. vomiting
 - d. fecal urgency
 - e. excessive gas/flatulence
 - f. tenesmus
4. Females of child bearing potential (WOCBP*) must not be pregnant or lactating at baseline visit (as documented by a negative urine pregnancy test with a minimum sensitivity of 25 IU/L or equivalent units of beta-human chorionic gonadotropin (Beta-HCG) at screening and urine pregnancy at baseline. **All female subjects will be considered to be of childbearing potential unless they are postmenopausal. WOCBP are defined as sexually mature women without prior hysterectomy, or who have had any evidence of menses in the past 12 months. However, women who have been amenorrheic for the past 12 or more months are still considered to be of childbearing potential, if the amenorrhea is possibly due to other causes, including prior chemotherapy, antiestrogens, or ovarian suppression. Postmenopausal women (defined as women who have been amenorrheic for at least 12 consecutive months, in the appropriate age group, without other known or suspected primary cause) or women who have been sterilized surgically or who are otherwise proven sterile (i.e., total hysterectomy, or bilateral oophorectomy with surgery at least 4 weeks prior to randomization) are not considered WOCBP. Subjects who have undergone tubal ligation are NOT considered as surgically sterile.*

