## 4. STUDY ENDPOINTS

### 4.1 Efficacy Endpoints

#### 4.1.1 Primary Efficacy Endpoint

**As per protocol**, the primary efficacy endpoint is clinical cure rate on TOC Visit (Study Day 5, 6 or 7). Clinical cure is defined as either of the following:

- No stools or only formed stools within a 48 hour period and no fever, with or without other enteric symptoms, OR
- No watery stools or no more than two soft stools passed within a 24 hour period with no fever and no other enteric symptoms except for mild excess gas/flatulence.

In addition, clinical deterioration by Study Day 5 or failure to achieve formed stool in  $\leq 3$  days (i.e., within 72 hrs from the time of first dose) is a clinical failure.

**As per FDA's OGD guidance**, the primary endpoint is clinical cure at the test of cure (TOC) visit on study Day 5, *with a window period of +/- one day*. In line with OGD, the protocol was designed such that the TOC visit should occur 24 to 72 hours after the last dose of study drug administration. After the study initiation, it was observed that some subjects were not able to complete the TOC visit within the above defined window period and a protocol deviation was filed to redefine the cut-off time point for evaluation of primary efficacy endpoint. Since, all the subjects were completing their diaries until the TOC visit and all the sites entered all diary data in the EDC that includes the data beyond the upper limit of window period for some subjects, decision was taken to consider 24 to 48 hour data for efficacy analysis. Thus, clinical cure rate was assessed on Visit-3 using subject's diary data from 24 to 48 hour period from the time of last dose when the drug is administered 3 times a day (TID) for 3 days in subjects with Travelers' Diarrhea (TD). Accordingly, clinical cure is re-defined as either of the following:

- No stools or only formed stools within a 48 hour period **from the last dose** with no fever, and with or without other enteric symptoms, OR
- No watery stools or no more than two soft stools passed within a 24 hour period **from the time of last dose** with no fever and no other enteric symptoms except for mild excess gas/flatulence.

This above decision was taken to standardize the data to be used for efficacy analysis and therefore there is no impact on the quality, safety & integrity of data due to the following reasons-

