1. The evaluation of primary efficacy endpoint will be based on patient reported data and not the visit dependent clinician's evaluation.

2. This is a planned deviation for efficacy evaluation and will be applied to all the subjects.

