### 1:1:1 Randomization

Thus, a total of 618 subjects need to be enrolled and randomized

assuming that the dropout rate from the randomized to mITT population does not exceed 15%.

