### **8.7 Analysis Conventions**

The following conventions will be applied to all data presentations and analyses.

- Summary statistics will consist of the number and percentage of responses in each level for categorical variables, and the sample size (n), mean, standard deviation (SD), median, minimum and maximum values for continuous variables.
- All mean and median values will be formatted to one more decimal place than the measured value. Standard deviation values will be formatted to two more decimal places than the measured value. Minimum and maximum values will be presented with the same number of decimal places as the measured value.
- The number and percentage of responses will be presented in the form xx (xx.x) where the percentage is in the parentheses.
- All summary tables will include the analysis population sample size (i.e., number of subjects).
- Change from baseline will be calculated as follows:  
Change = (baseline value)–(post-baseline value).
- All listings will be sorted for presentation by treatment and subject.
- Date variables will be formatted as DDMMYYYY and time format is HH:MM for presentation.
- SAS Version 9.4 or higher will be the statistical software package used for all data analysis.
- A separate document with programming instructions will be prepared that will describe the derivation of these populations, before the database lock (DBL) or treatment unblinding for

the study. This document will also include specifications and programming instructions for creating analysis datasets. An analysis dataset is a dataset created to answer specific analysis purposes which will include all the variables from raw dataset, population flags, treatment flags and some derived variables as per requirement.

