### APPENDIX III

**Analysis Data Specification:** Detailed plan for derived variables (have specified attributes and definitions) to create TFLs on Subject-Level data and Basic Data Structure of domain wise analysis data will be prepared in a separated spread sheet document.

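### Cure criterion 2 joins its two stool limits with 'or', so read literally it can score ongoing diarrhoea as clinical cure

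*Protocol*

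**What the plan says.** Protocol 7.2 gives two alternative routes to cure. The first requires 48 hours with no stools or only formed ones, and no fever. The second sets its stool condition as "No watery stools or no more than two soft stools passed within a 24 hour period" and adds no fever and no enteric symptom beyond mild gas. The same connective appears wherever criterion 2 is visible: in the protocol synopsis (objectives and endpoints), protocol 2 and 7.2, and SAP 2.1 and 4.1.1. SAP 4.1.1 then changes the endpoint ("Accordingly, clinical cure is re-defined as either of the following"), anchors both windows to the last dose, and keeps 'or'.

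A further clause makes deterioration by Day 5, or no formed stool within 3 days (72 hours from first dose in the SAP), a clinical failure.

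Protocol 4.1 states: "Diarrhea is defined as the passage of at least 3 episodes of unformed stools in a 24-hour period". It also says that "both soft and watery stools are unformed and abnormal".

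SAP 4.1.1 adds: "The evaluation of primary efficacy endpoint will be based on patient reported data", as opposed to a clinician's assessment at the visit. The programming rules are in separate documents. SAP 8.7 says of one: "This document will also include specifications and programming instructions for creating analysis datasets". SAP Appendix III describes another: "Detailed plan for derived variables (have specified attributes and definitions". Neither is visible.

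**The concern.** Criterion 2 is the only route by which a subject who still passes unformed stools can be a cure, so its stool limit has to separate recovery from continuing diarrhoea. With a literal 'or', each limb stands without the other's limit. Having no watery stools is enough however many soft stools there are, and having at most two soft stools is enough however many watery stools there are. The rule then passes some patterns that are worse than ones it fails.

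Because cure is computed from diary entries, no clinician's judgement stands between the written rule and the classification. If failures are re-scored as cures at the same rate in every arm, differences between arms shrink. That makes equivalence easier to declare and superiority over placebo harder to show. If the rates differ between arms, either result can move in either direction.

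**Working it through.** The plan states no figure for this point, so there is none to reproduce.

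**1. Logic.** Let w and s be the numbers of watery and soft stools in 24 hours. The rules compared are:
- literal: w = 0 or s ≤ 2
- alternative: w = 0 and s ≤ 2
- diarrhoea (protocol 4.1): w + s ≥ 3

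Over a grid of 0–6 watery by 0–6 soft stools (49 patterns; the grid is an assumption):

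| Rule | Patterns passed | Of these, diarrhoea |
|---|---|---|
| 'or' | 25 | 19 |
| 'and' | 3 | 0 |

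The 22 patterns that change status are 4 with soft stools only (3 to 6) and 18 with at least one watery stool. All of the first 4 and 15 of the 18 are diarrhoea, giving 19. The other 3, as (w, s), are (1,0), (1,1) and (2,0). Under 'or', (0,6) and (6,0) pass while (1,3) fails. These are counts of patterns, not frequencies of patients. The grid sets the counts, but diarrhoeal patterns pass under 'or' and none passes under 'and' whatever the grid.

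**2. Do the other clauses close the gap?** Take a subject with one formed stool within 72 hours of first dose, then three or more soft stools in the assessed 24 hours, no fever and only mild gas. The formed-stool requirement is met, and so are the fever and symptom conditions. Only the deterioration clause could make this subject a failure, and the visible text does not define deterioration.

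**3. Direction of effect (illustration on assumed values, with 'and' taken as the intended endpoint).**
- Size: "1:1:1 Randomization" (SAP 7.2) gives 618/3 = 206 per arm. Less 15% dropout, 206 × 0.85 = 175. This is an mITT count; the PP size is redacted, so 150 and 125 are shown as well.
- Re-scoring a share r of failures as cures changes a cure rate p to p + r(1 − p).
- Equivalence (SAP 7.5.1): difference ± [1.645·se + (1/N_T + 1/N_R)/2] must lie within ±0.20.
- Superiority: two-sided pooled Z-test with Yates correction, p < 0.05, active arm higher.
- All probabilities come from exact enumeration of two binomials.

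Probability of declaring equivalence when true cure is 0.60 (test) and 0.80 (reference), that is, at the margin:

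| Per arm | r = 0 | 3% | 5% | 10% |
|---|---|---|---|---|
| 175 | 3.8% | 5.0% | 6.0% | 9.0% |
| 150 | 3.8% | 4.9% | 5.7% | 8.3% |
| 125 | 3.7% | 4.7% | 5.4% | 7.7% |

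The probability passes 5% at r of about 3.0%, 3.4% and 3.9% respectively. At 175 per arm that is 0.03 × 0.40 × 175 = 2.1 test subjects and 0.03 × 0.20 × 175 = 1.05 reference subjects expected. With other base rates 0.20 apart, from 0.50/0.70 to 0.65/0.85, r = 10% gives 8.6% to 9.5%.

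Unequal re-scoring at 175 per arm (test/reference): 2%/5% gives 3.5%, 5%/10% gives 3.85%, and 10%/5% gives 13.0%.

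Superiority power for 0.75 against 0.60, 175 per arm: 82.5%, 80.7%, 79.5% and 76.3% at r = 0, 3, 5 and 10%. Unequal re-scoring (active/placebo) gives 86.5% at 10%/5% and 66.9% at 5%/10%.

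**The case against.** The strongest reply is that this is loose drafting, not a demonstrated analysis error. 'Or' after a negative can mean 'neither … nor', and the unseen specifications may already apply both limits. Part of the SAP is also redacted. This stands as a limit on what can be claimed: misclassification arises only if the rule is programmed as written. It does not settle the reading, because the text those specifications implement leaves it open for the primary endpoint.

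The second reply is that few subjects could be affected. Frequent watery stools without urgency, cramps or nausea would be unusual, and a relapse after a formed stool might be called deterioration. The symptom condition does narrow the gap. The deterioration clause may or may not, since it is undefined.

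Third, the cure rates, re-scoring shares and PP size are assumed, the 5% crossing applies only with the true difference at the margin, and unequal re-scoring can lower as well as raise the chance of declaring equivalence. All of this is right, so the figures show direction, not expected size.

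Finally, reasons for failure are tabulated by criterion (SAP 7.5.1) and stool counts are listed by subject (SAP 8.5), so odd cures could be noticed. That helps detection, but it does not fix the rule in advance.

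**Conclusion.** The concern holds. As written, the stool condition of criterion 2 admits patterns that the protocol itself calls diarrhoea: 19 of the 25 patterns it passes on the 0–6 grid, against none of 3 with 'and'. The fever, symptom and failure clauses narrow this gap without closing it. The conclusion about the wording needs no numerical assumption.

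The effect on the trial's results cannot be determined from the documents and may be small. It depends on how the derivation is programmed, how many symptom-free subjects have such patterns, and how they are spread across arms. The point should be fixed but is not shown to invalidate the analysis. It matters because it concerns the primary endpoint, which was already redefined after the study began.

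**What to change.** In SAP 2.1 and 4.1.1, and in the derivation specifications under SAP 8.7 and Appendix III, join the two stool limits of criterion 2 with 'and'. Before doing so, check the intended reading against the FDA guidance that SAP 4.1.1 cites. If a literal 'or' is intended, say so and explain why patterns that meet the protocol's definition of diarrhoea count as cure. Date the change before database lock and unblinding.

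Count in blinded pooled data the subjects whose status differs between the two readings, and report that count by arm after unblinding. As a lesser point, repeat the failure clause beside the redefined criteria in SAP 4.1.1 and confirm that it overrides a met cure criterion, which is already the likeliest reading.

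The cost is one SAP version with its rationale and, if the program follows the literal text, a one-word change to the derivation. The diary data are already in the EDC. Correcting the protocol synopsis and sections 2 and 7.2 needs ethics committee acceptance (protocol 10.2). It can wait for the next amendment, or the change can be recorded as an SAP clarification.
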